### PK Samples Handling

[figure not shown]
Plasma will be prepared from the blood samples and split into two aliquots (one for backup) for analysis of plasma concentrations of FAB122 and riluzole using a validated LC/MS/MS assay method. Instructions for handling, shipment and storing of the PK samples will be described in a separate study PK laboratory manual. Plasma concentrations will be measured using validated bioanalytical methods and according to the bioanalytical laboratory's Standard Operating Procedures (SOP). Qualitative/comparative assessments of metabolite profiles will be performed.

## 7. STUDY INTERVENTIONS

### 7.1. Investigational Medicinal Product(s) (IMP) Description

Compound name: FAB122  
INN/generic name: edaravone  
Synonyms: norphenazone; methylphenylpyrazolone; norantipyrine  
IUPAC name: 3-methyl-1-phenyl-4, 5-dihydro-1H-pyrazol-5-one  
CAS name: 5-Methyl-2-phenyl-1, 2-dihydropyrazol-3-one (CAS Registry No. 89-25-8)  
Molecular formula: C10H10N2O  
Chirality: FAB122 has no chiral centre

Structural formula:

Molecular weight: 174.20 g/mol  
Appearance: off-white to white powder  
Solubility: sparingly soluble in water, soluble in acetic acid and methanol, limited solubility in ethanol  
Hygroscopicity: FAB122 is not hygroscopic

Each sachet of the active treatment contains the following composition given in the table 4:

**Table 4: The theoretical quantitative composition of FAB122 granules for oral solution in sachet**

Component	Amount/sachet
FAB122	100.0 mg
Spray dried mannitol 200	621.8 mg
Disodium hydrogen phosphate dihydrate	363.6 mg
Sodium Laurilsulfate (SLS)	5.5 mg
Total	1090.9 mg

The active ingredient and the investigational drug have been produced complying the Good Manufacturing Practices of the European Union for active pharmaceutical ingredients and ICH Q7A guidelines.

Study treatment is supplied as granules for oral solution, 100 mg FAB122 or placebo per sachet, to be dissolved in about 100 ml water approximately and stirred slightly by a teaspoonful. Study treatment must be administered immediately after its dissolution.

First dosing will be administered at the study site and patients will be instructed about study treatment administration.

Study treatment should be administered once a day at about the same time each day. Dosing needs to be done each morning under fasting conditions. This implies taking the dose: at least two (2) hours after a meal or snack and 30 min after a drink AND no eating or drinking for at least one hour post dosing. If a subject misses a dose, the missed dose should be taken as soon as possible taking the fasted conditions into account if feasible. If the time period until the regular dosing time for the next dose is less than 4 hours, then the missed dose should be skipped, and the normal dosing schedule should be resumed. The next dose should not be doubled in order to make up for the missed dose.

The study medication is to be stored in the refrigerator at a temperature between 2 - 8 °C. Temperature excursions are permitted at 8-25°C not exceeding 72 hours. Please contact the sponsor in case the temperature excursion is on different conditions from the ones mentioned before.

Study treatment could be given via gastric gavage and feeding tube if applicable.

### **7.1.1. Packaging and Labelling**

The label(s) for the investigational product and placebo will include all information according to GMP Annex 13. Additional information may be included on the label as applicable per local regulations.

### **7.1.2. Blinding of IMP**

Verum and placebo are identical and unrecognizable sachets by form size, weight, and colour, and will be indistinguishable to patients and investigators.

### **7.1.3. Compliance with Trial Treatment**

Patients will be instructed to return all used and unused medication at each study visit. The number of sachets dispensed and returned will be registered by the investigator at each visit to obtain information on patients' compliance. The patient will be considered compliant with treatment when 80%-120% of the total scheduled doses since the last clinic visit are administered.

All investigational products used in this study will be monitored for compliant usage throughout the trial by the sponsor or their designee.

### **7.1.4. Accountability of the Trial Treatment**

Adequate supplies of the IMP will be provided to the site. Study drug should be stored in the original package under conditions as stated on the product label, in a secure, temperature-monitored, locked area, under the responsibility of the Investigator or other authorized individual until dispensed to the subjects.

The pharmacy of the site must maintain accurate records of the receipt of all study drug, including date received, lot number, expiration date if applicable, amount received, condition of the package, and the disposition of all study drug.

Current dispensing records will also be maintained, including the date and amount of medication dispensed and the identity of the subject receiving the medication.

At the end of the study, it must be possible to reconcile delivery records with those of used, partially used and returned stocks.

All used and unused IMP must be returned to the storage/distribution facility after the study is completed.

In case of sanitary restrictions or if a patient cannot attend one study visit, following local regulation, IMP can be delivered directly to patient's home, as per site internal procedure or through a validated direct to patient service provided by the sponsor. For more details, please refer to the IP Manual.

### **7.1.5. Concomitant Medication**

The permitted concomitant medication for ALS patients' management (such as symptomatic treatment of muscle spasms, pain, insomnia, dysphagia and emotional instability) are listed in the Annex 3.

Treatment of ALS impairments (nutrition, respiration, motricity, communication) will be done with a multidisciplinary approach and accordingly to European Federation of Neurological Societies (EFNS) Guidelines for ALS patients' management.

### **7.1.6. Post-trial Treatment**

Once patients have completed the study (max week 72) and if potential clinical benefit is achieved, patients could be enrolled in an open-label one group extension study and FAB122 will be given for all included patients.

## **7.2. Other Treatments (non-IMPS)**

Riluzole (100 mg/day or less) may be used as background (add-on) therapy. Patients on riluzole should be on stable doses  $\geq 30$  days prior to the baseline visit and this dose should be maintained during the entire trial. It will not be allowed to initiate riluzole therapy during the trial.

---

## 8. PARAMETERS AND METHODS OF ASSESSMENT

### 8.1. Parameters

#### 8.1.1. ALSFRS-R

The ALSFRS-R is a validated 12-item questionnaire designed to evaluate the functioning of respiratory, bulbar, fine and gross motor function in ALS patients. The total score ranges from 48 (no limitation in daily activities) to 0 (total inability). The patients will be asked to complete the ALSFRS-R questionnaire at each in-clinic visit on Screening, Baseline, and weeks 4, 12, 24, 36, 48, 60, and 72, as well on each phone call on weeks 8, 16, 20, 28, 32, 40, and 44. The total score of the ALSFRS-R and the score of each subdomain will be recorded in the eCRF by the investigator or designee.

#### 8.1.2. Survival Time

If a patient dies during the 72 weeks of participation, the date of death will be recorded in the eCRF. If a patient reaches the criteria for respiratory insufficiency (tracheostomy or the use of non-invasive ventilation for >20 hours per day for >10 consecutive days), the date this criterion was met will be recorded in the eCRF and the patient will no longer be part of the study.

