## 4. STUDY DESIGN

Multicenter, multinational, double-blind, randomized (2:1), placebo-controlled Phase III study to investigate the efficacy and safety of 100 mg FAB122 (former TW001) once daily as oral formulation in ALS patients.

Subjects will be screened to assess whether they comply with all enrolment criteria. Approximately 300 patients will be randomized to 100 mg FAB122 or matched placebo in a 2:1 ratio. Patients will be stratified by;

- 1) their ALS progression rate at the start of the study (the slope ALSFRS-R score from time of first symptoms till Screening <1.0 vs.  $\geq 1.0$ ),
- 2) additional co-medication for ALS (a. riluzole, b. no riluzole).

Riluzole (100 mg/day or less) may be used as background (add-on) therapy. Patients on riluzole should be on stable doses at the start of the trial and for at least 30 days before the initiation of the study drug. It will not be allowed to initiate riluzole therapy during the trial. Additional supportive Standard Of Care (SOC) treatments will be allowed in all patients and will be standardized as much as possible.

Subjects will receive double-blind treatment up to a maximum of 72 weeks. The study is planned to continue until the last randomized subject has reached 48 weeks of follow up (or has reached an intercurrent event) AND the first one third of the subjects randomized (100) have reached 72 weeks of follow up (or has reached an intercurrent event). Subjects who discontinue treatment before week 72 will be followed as much as possible according to the planned visit schedule. In case of sanitary restrictions due to COVID-19 pandemic, home visits might be performed (for more details, see annex 4).

[figure not shown]
Subjects will visit the clinic at Screening, Baseline, Week 4, Week 12, and every 12 weeks thereafter. Monthly telephone visits are performed in between the visits to the clinic until Week 48.

Blood sampling for FAB122 plasma concentrations will be done in ~90 subjects treated with the study drug.

After a subject completed the study (max at 72 weeks), he/she will be offered the possibility to roll over in an open label extension trial in which all subjects will be offered to receive FAB122.

The end of the trial will correspond to the last subject last visit per the trial schedule.

The study flowchart is presented in the Figure 2.

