#### 6.5. Early Discontinuation/Withdrawal of Participants

Subjects may withdraw consent at any time for any reason or be dropped from the trial at the discretion of the investigator should any untoward effect occur. In addition, a subject may be withdrawn by the investigator or the Sponsor if enrolment into the trial is inappropriate, the trial plan is violated, or for administrative and/or safety reasons.

In this trial, a subject may discontinue from treatment but continue to participate in the regularly scheduled activities, as long as the subject does not withdraw consent. Once a subject has discontinued treatment, he/she may be allowed to start treatment again after consultation with the investigator, if discontinuation of treatment is  $\leq$  2 weeks.

A subject must be discontinued from the trial for any of the following reasons:

- The subject withdraws consent.
- The subject has a medical condition or personal circumstances which, in the opinion of the investigator and/or Sponsor, places the subject at unnecessary risk if participation in the trial is continued.
- The subject reaches the criteria for respiratory insufficiency (tracheostomy or the use of non-invasive ventilation for >20 hours per day for >10 consecutive days),

A subject must be discontinued from study treatment (but should continue to be monitored in the study) for any of the following reasons:

1-The subject becomes pregnant during the study.

2-The subject's investigator considers it is in the best interest of the subject to discontinue including worsening or disease progression if the investigator considers that it is in the patient's best interest the initiation of any standard of care treatment prohibited in the study

3-Serious adverse event considered related to the IMP

4-Severe Neurotoxicity considered related to the IMP

5-Any other severe adverse event considered related to the IMP at the discretion of the investigator.

6-Acute renal failure (creatinine clearance of less than 30 mL/min as calculated by the Cockcroft Gault equation)

7-Severe liver disorder defined as:

- ALT/AST  $\geq$  3xULN and bilirubin  $\geq$  2xULN ( $>35\%$  direct bilirubin)
- ALT/AST  $\geq$  8xULN
- ALT/AST  $\geq$  3xULN and with symptoms believed to be related to liver injury or hypersensitivity.
- ALT/AST  $\geq$  3x baseline ALT/AST and with symptoms believed to be related to liver injury or hypersensitivity.

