### **11.3.3. Subject Disposition**

Subject disposition (analysis population allocation, entered, discontinued, along with primary reason for discontinuation) will be summarized using frequency and percent for

---

both treatment and follow-up phase. A summary of subjects screened and enrolled will be provided.

A subject is considered to complete the study if he/she completed the 72 week period OR if she/he completed at least 48 week at study completion (i.e. after the last subjects have completed the study up to at least 48 week). Withdrawal from treatment or protocol deviations will not necessarily preclude from recording the respective follow-up information. Efforts will be made to follow all subjects up to 72 or 48 weeks after start of treatment (or to study end if that occurs earlier) and collect data as planned.

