### 11.4. Study Estimand and Handling of Missing Data

To be noted that in this study all efforts will be made to ensure collection of data up to week 48 for all randomized subjects and at least for 100 subjects up to week 72 regardless of treatment withdrawal or protocol deviations.

As per the ICH E9(R1) (*draft addendum on estimands and sensitivity analysis in clinical trials*), the plan for the assessment of the Primary endpoint (PEP) is described here after using the 4 attributes of the estimand:

1. Population: ALS patients fulfilling the selection criteria, as described in section 5 of this protocol
2. Primary endpoint (PEP): Change from baseline in Amyotrophic Lateral Sclerosis Functional Rating Scale – Revised (ALSFRS-R) score after 48 weeks (see sections 3.2.1 and 11.3.4.1)
3. Intercurrent events (IE): The assumptions and expectations on the relevant intercurrent for this study have been based on the publication of a similar trial (Cudkowicz et al., 2013)
4. Accordingly, the following situations have been identified:
  - a. No treatment initiation with the IMP: exclusion from the main analysis with the mFAS population.
  - b. Treatment discontinuation because of adverse events: expected rates  $\approx 3$  (control arm) - 7% (experimental arm).
  - c. Treatment discontinuation because of lack of efficacy: expected rates  $\approx 5$  (control arm) 10% (experimental arm).
  - d. Other treatment related reasons (i.e. due to efficacy or safety issues). To this category will apply other treatment related reasons that those specified in "b" and "c", even that, *a priori*, no potential scenarios are foreseen at the moment of the planning.
  - e. Rescue medication. No clear prevalence rates can be ascertained, but differential higher rates are expected in placebo. This situation is likely to be closely related to IE #c.
  - f. Non treatment-related reasons, others than specified in this list of IE: very low expected rates (i.e.  $\le 1\%$ ). This will also situations like patients moving (not because bad prognosis) to another location or death for completely treatment-unrelated reasons.
  - g. Related death (or death with unknown reasons): it is expected that the rate of death at 52 weeks will be lower than the observed in that trial ( $< 17\%$ ). A non-substantial but lower rate is expected in the experimental arm.

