The primary strategy for handling the IE will consist of the "Treatment Policy" strategy applied for all these intercurrent events, i.e., the efficacy observed assessment will be used regardless of the intercurrent event. Therefore, overall the amount of missing data generated will be a very small. For these cases a placebo (copy from reference) multiple imputation will applied. A total of 20 imputed data sets will be created.

However, it is noted that the "Treatment Policy" strategy will not be applicable for terminal intercurrent events such as death (IE #g) or when there are real lost to follow-up cases after doing all efforts to retrieve the data (some cases in IE #f). For cases with missing data in IE #f, the same general approach as described above will be implemented. For related death (IE #g) it is proposed to use a "Composite strategy" and thus a conservative scenario using a 95th worst percentile combined with multiple to avoid variance artefactual shrinking.

---

- h. Population-level summary: the change from baseline in ALSFRS-R score after 48 weeks (primary time point), using a linear mixed modelling for repeated measures. The model will include factors for treatment, time, treatment-by-time interaction, and concomitant use of riluzole (yes/no) as fixed effects and baseline ALSFRS-R score and slope of disease progression (based on change in ALSFRS-R score) as (random) covariates (see section 11.3.4.1)).

To evaluate the impact of missing data and of the handling methods, a number of sensitivity analyses will be performed for the primary endpoint:

- **As treatment multiple imputation:** For any subject with missing values, the estimates for the missing assessments will be based on the actual treatment group of that subject. One hundred imputations will be performed.

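### SAP 5.6.1 limits placebo-reference imputation to events without a known cause, against the protocol and its own sentence, so patients who exit at respiratory insufficiency have no clear primary-analysis rule

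*Protocol*

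**What the plan says.** **Exit.** Protocol 6.5 has two lists. The first opens "A subject must be discontinued from the trial for any of the following reasons" and includes "The subject reaches the criteria for respiratory insufficiency". The second opens "A subject must be discontinued from study treatment (but should continue to be monitored in the study) for any of the following reasons", and RI is not in it. Protocol 8.1.2 confirms the consequence: "the date this criterion was met will be recorded in the eCRF and the patient will no longer be part of the study". Table 1, footnote 1 also ends participation at an intercurrent event.

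**Estimand.** Protocol 11.4 says that "all efforts will be made to ensure collection of data up to week 48 for all randomized subjects". It describes Treatment Policy as meaning that "the efficacy observed assessment will be used regardless of the intercurrent event", with exceptions for terminal events, of which death is the example, and for real loss to follow-up. SAP 5.2 closes that list: only death and real loss are terminal, and after any other event data may still be obtainable. Neither list of intercurrent events names RI. Both have catch-all entries for other reasons, treatment-related or not.

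**Imputation.** Protocol 11.3.4.2 applies placebo-reference imputation in both arms to early discontinuations without later data, whatever the reason. SAP 5.6.1 says the same and then restricts it, within the same sentence, to events whose cause is unknown. The worst-percentile composite in SAP 5.2 is for death and for patients lost after reasonable contact attempts have failed. SAP section 6, which lists departures from the protocol, does not mention the restriction. For CAFS, SAP 5.6.2 sends survivors with a missing week-48 score to the rule in 5.6.1.

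**The concern.** RI is severe, foreseeable and part of a key secondary endpoint. Yet the primary analysis can be read in two ways for the patients who reach it: imputed from placebo, or left to the mixed model as missing at random. Nothing in the SAP settles which applies, so the choice would be made outside the plan. Because CAFS borrows the rule, the ambiguity reaches the second step of the confirmatory hierarchy as well.

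There is a separate design question behind it. The scores are missing because the protocol stops collecting them, while the estimand is written as if they would be available.

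**Working it through.** **1. The texts side by side, for an RI exit with no week-48 score**

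| Source | Condition | Result |
|---|---|---|
| Protocol 11.3.4.2 with 11.4 | any reason; catch-all categories apply | placebo-reference imputation |
| SAP 5.6.1, main clause | any reason | placebo-reference imputation |
| SAP 5.6.1, bracket taken literally | unknown cause only; RI is known and dated | no imputation; missing at random (MAR) in the mixed model |
| SAP 5.2 composite | death, or loss after failed contact | not met: the exit is required by protocol |
| SAP 5.6.2, CAFS | survivors use the 5.6.1 imputation | presupposes that 5.6.1 imputes survivors |

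The third row contradicts the first two. The last row favours the wide reading.

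**2. The plan's own figure** (Protocol 11.2: difference 3.0, SD 7.5, 200 and 100 patients, two-sided 5%)

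SE = 7.5 × √(1/200 + 1/100) = 0.919. Power = Φ(3.0/0.919 − 1.96) = 90.4%, against 90% stated. Reproduced.

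**3. Patients affected.** The documents give no RI rate. Assume 3% to 8% by week 48: 0.03 × 300 = 9; 0.08 × 300 = 24. One later score is planned, at the End-of-Trial visit 7 to 14 days after withdrawal (Protocol 6.5), and SAP 5.3 maps it to the next scheduled visit. It counts as week 48 for about 4/48 = 8% of exits if timing is even, and up to about 17% in the simulation below, where risk rises over time. So 83% to 92% have no week-48 score: 9 × 0.83 = 7.5 and 24 × 0.917 = 22, or about 7 to 22 patients.

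**4. What the choice of rule is worth**

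By hand, ignoring earlier visits, FAB122 exits move from a mean of −9 to the placebo mean of −12. The shift is the exit rate × 3.0: 0.03 × 3.0 = 0.09, or 0.08 × 3.0 = 0.24. Both rules in fact condition on scores before exit, which shrinks this.

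A simulation that conditions on them used 350 to 400 runs per scenario, 200 versus 100 patients, linear decline of 9 versus 12 points, SD 7.5 at week 48, residual SD 2 and visits every 4 weeks. All RI inputs were assumed: hazard proportional to exp(0.12 × decline), set to 3% or 8% in placebo; FAB122 hazard ratio (HR) 0.5, 1 or 2; no later score, no later score with a 3-point drop at RI, or one later score with that drop. MAR minus placebo-reference, with the drug effect continuing after RI and all earlier visits used:

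| RI rate, placebo | HR 0.5 | HR 1 | HR 2 |
|---|---|---|---|
| 3% | 0.004–0.007 | 0.009–0.015 | 0.022–0.030 |
| 8% | 0.014–0.019 | 0.029–0.045 | 0.054–0.084 |

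Using only the last three visits gave 0.007 to 0.112. If the drug effect stops at RI, the range was 0.005 to 0.107. With no drug effect it was 0.000 and −0.001. Monte Carlo error was at most 0.003.

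Largest case: 0.112/0.919 = 0.12 SE. Power at 3.0 − 0.112 = 2.888 is Φ(2.888/0.919 − 1.96) = 88.2%.

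Compared with full follow-up, placebo-reference was off by 0.00 to 0.22 points and MAR by 0.00 to 0.31. MAR was often closer if the drug effect continues, and placebo-reference was mostly closer if it stops, so the simulation does not choose between them. For CAFS (function only, no deaths), the last-common-visit route in SAP 9.1 and the imputed route differed by −1.8 to +0.6 in a mean-rank difference of about 33.

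**5. Exit against estimand.** Protocol 11.4 aims at week-48 data for every randomized patient and uses scores observed after an event. Protocol 6.5 and 8.1.2 end collection at RI, apart from the End-of-Trial visit. SAP 5.2 classes RI, by omission, as an event after which data may be collected.

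**The case against.** Much of the opposing case stands.

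- **Follow-up promises.** A reader might infer that two further passages contradict the exit: "Subjects who discontinue treatment before week 72 will be followed as much as possible according to the planned visit schedule" (Protocol 4) and "Efforts will be made to follow all subjects up to 72 or 48 weeks after start of treatment" (Protocol 11.3.3). They do not. Both concern patients who stop treatment, and Protocol 6.5 keeps that group apart from patients who leave the trial. Protocol 11.4 is also an aim rather than a guarantee, and its terminal events are an open list. The rationale for efficacy endpoints pairs RI with death, so the exit may be deliberate for survival time. What remains is a tension with 11.4 and with the closed list in SAP 5.2.
- **The protocol already has a rule.** It does: its catch-all categories and 11.3.4.2 lead to placebo-reference imputation. The fault in the imputation rule therefore lies in the SAP.
- **MAR is only the literal reading.** The SAP never assigns it to these patients, and the CAFS section points the other way. That speaks to intent, but the restricting words remain in the primary-analysis text.
- **Existing cover.** The as-treatment, hybrid and tipping-point analyses can include RI exits, and CAFS has an early-discontinuation rule. These help interpretation but do not settle the primary rule. The completer analysis keeps deaths and is silent on RI exits.

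**Conclusion.** The point holds as a fault in the SAP text. SAP 5.6.1 contradicts itself and Protocol 11.3.4.2 on how missing scores after a known, severe outcome enter the primary analysis, and SAP section 6 does not say so. Separately, the mandatory exit sits uneasily with Protocol 11.4 and SAP 5.2.

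The effect is probably small: at most about 0.11 points against an assumed effect of 3.0, or 0.12 SE. Confidence is high for the text and lower for the numbers, because the RI rate, hazard form, hazard ratios and drop at RI are all assumed. With no drug effect the two rules agree, so no type I error inflation is shown.

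A reader might infer larger stakes by treating RI exits as lost to follow-up, which would bring in the worst percentile. Taking that value as −12 − 1.645 × 7.5 = −24.3 and ignoring earlier visits, assumed exit rates of 5% placebo and 10% FAB122 give a difference of 2.08 points and 56% power; 10% and 5% give 3.47 points and 94%. The documents do not support that reading. SAP 5.2 requires failed contact attempts, and a dated exit required by the protocol is not that. These figures should not be used to judge severity.

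**What to change.** (a) In SAP 5.6.1, delete the restriction to unknown causes, so that placebo-reference imputation covers RI exits with no week-48 score, as in Protocol 11.3.4.2. CAFS then follows through SAP 5.6.2. Word the condition so that a single End-of-Trial score does not take a patient out of the rule.

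(b) Name RI in SAP 5.2 under Treatment Policy, use any score observed after RI, including the End-of-Trial visit, and state how RI exits enter the completer analysis.

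(c) List any remaining difference from the protocol in SAP section 6.

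Items (a) to (c) cost only wording. SAP section 1 requires the plan to be final before database lock and unblinding, so they should be settled by then.

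(d) Reconcile Protocol 6.5, 8.1.2 and Table 1 footnote 1 with 11.4. If the protocol can still be amended, preferably keep collecting ALSFRS-R and vital status after RI, for patients who do not withdraw consent, by the telephone route already in Protocol section 6. SAP 5.1 accepts telephone scores as equal in quality. Also confirm whether the survival follow-up form cited in SAP 5.6.2 continues after RI. This needs ethics and authority approval and a few calls for an assumed 9 to 24 patients. Some may be unable to answer, and their scores would follow (a).

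No rule on treatment after RI is proposed; that is for the sponsor to reconcile.
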